7.2 Safety outcomes

Safety outcomes will be analysed using the safety analysis population.

7.2.1 Placement of events by study phases

Adverse events are placed in study phases (see Section 5.2 for definitions) based on the start date.

In case of partial start dates, the following approach is used:

- **Missing day only**: The event is placed in the earliest phase that overlaps the given month and year for the event, excluding any phases that start after the end date of the AE (if specified).
- **Missing day and month only**: The event is placed in the earliest phase that overlaps the given year for the event, excluding any phases that start after the end date of the AE (if specified).
- **Missing start date:** The event is placed in the treatment phase, unless the end date of the AE is specified and is before randomisation, in which case the event is placed in the screening phase.

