# 13 SAFETY REPORTING

GCP requires that both investigators and sponsor follow specific procedures when notifying and reporting adverse events/reactions in clinical trials. These procedures are described in this section of the protocol. Section 13.1 lists definitions, section 13.2 gives details of the institution/investigator responsibilities and section 13.3 provides information on MRC CTU responsibilities.

AEs are collected from the time the informed consent form is signed at screening until follow-up is completed or the participant withdraws from the trial. If a patient is found to be ineligible for the trial at screening, or chooses not to be randomised, no further AE data should be collected from that point.

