5.2 Treatment and follow-up phase definitions

For the purpose of analysis, the treatment and follow-up phases for an individual patient will be defined as follows:

Screening phase

- Start: date of screening consent
- o End: day before randomisation

• Treatment phase

- o Start: date of randomisation.
- End: date of last dose of any TB treatment defined as last dose of any TB treatment (including retreatment for relapse), plus 7 days.

• Follow-up phase

- o Start: the day after the end of the treatment phase.
- End: date of the last patient contact (scheduled or unscheduled visit, or other contact e.g. phone call).

The treatment phase includes any extension of treatment or retreatment, and so the Allocated Treatment phase is defined as follows:

• Allocated Treatment phase

- Start: date of randomisation.
- End: date of last dose of trial treatment defined as last dose of allocated regimen or last dose before the addition of a new drug, whichever happens sooner, plus 7 days.

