This analysis will be conducted on the whole study period, and separately for follow-up censored at Week 76. It will also be repeated comparing bedaquiline and non-bedaquiline regimens (Regimens A and B vs C and D) and comparing Regimen B_{mox} and Regimen C, and Regimen B_{lev} and Regimen C. A descriptive analysis will consider deaths by cause, as adjudicated by an independent review committee. In addition to the comparisons detailed above, analyses of the whole study period (up to Week 132) will include comparisons of Regimen C with Regimen D. Comparisons of Regimen C and Regimen D using data up to Week 76 were carried out at the time of the primary analysis but considered exploratory.

7.2.3 Proportion of patients experiencing a grade 3 or greater adverse event, as defined by the DAIDS criteria, during treatment and follow-up

The difference in proportion of patients experiencing a grade 3 or greater adverse event, as defined by the DAIDS criteria¹⁰, during treatment and follow-up, between Regimen B and Regimen C, between Regimen B_{mox} and Regimen C, between Regimen B_{lev} and Regimen C, between Regimen B and Regimen D, and between Regimen B and Regimen A, with corresponding two-sided 95% confidence intervals and p-values will be estimated (see Section 6.1.1). The analysis will be stratified by randomisation protocol (as defined in Section 1.6) and HIV status with three strata: HIV negative, HIV positive with CD4 count less than 350 cells/mm³, and HIV positive with CD4 count more than or equal to 350 cells/mm³.

This analysis will be conducted on the whole study period, the study period censored at Week 76, and separately for each phase (Treatment censored at Week 76, and Allocated treatment).

Comparisons will be repeated in subgroups according to HIV infection status. In addition the proportion of participants with cardiac events, hearing loss and hepatotoxicity by Week 76 and Week 132 in Regimen C and Regimen D will be compared to Regimen B.

In addition to the comparisons detailed above, analyses of the whole study period (up to Week 132) will include comparisons of Regimen C with Regimen D. Comparisons of Regimen C and Regimen D using data up to Week 76 were carried out at the time of the primary analysis but considered exploratory.

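### Adverse events dated only to the month or year of randomisation are placed in screening, so on-treatment events can be lost from the phase-based safety analyses

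*SAP*

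**What the plan says.** SAP 7.2.1 places adverse events in study phases by start date and gives three rules for incomplete dates.

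- Day missing: "The event is placed in the earliest phase that overlaps the given month and year for the event".
- Day and month missing: "The event is placed in the earliest phase that overlaps the given year for the event".
- No start date at all: "The event is placed in the treatment phase, unless the end date of the AE is specified and is before randomisation", in which case it goes to screening.

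The first two rules carry one exclusion, "excluding any phases that start after the end date of the AE (if specified").

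SAP 5.2 defines the phases. Screening comes first ("Start: date of screening consent"; "End: day before randomisation"). The Treatment and Allocated Treatment phases both start on the date of randomisation. Screening is a category that can hold real events: under Protocol section 13, "AEs are collected from the time the informed consent form is signed at screening".

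SAP 7.2.3 compares "The difference in proportion of patients experiencing a grade 3 or greater adverse event, as defined by the DAIDS criteria", over treatment and follow-up. It runs this for the whole study period, for that period censored at Week 76, and separately for the Treatment phase (censored at Week 76) and the Allocated Treatment phase. SAP 9.3.5 tabulates SAEs and grade 3 or greater events for the whole study period and the same two phases. Neither section says whether the whole study period includes screening.

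**The concern.** Screening normally ends in the month in which treatment starts, and almost always in the same calendar year. For an event dated only to that month or year, the first overlapping phase is therefore screening. The end-date exclusion does not help: it removes phases that begin after the event ended, so it can remove later phases but never screening for an event that ended on treatment.

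The result is out of order with the rest of the list. With no start date, the event counts as on treatment. Once the year is known, the same event moves to screening, although the year does not show that onset came before the first dose.

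What is at stake is the count of on-treatment harm in each arm. Events in the month of randomisation occur when all the intensive-phase drugs have just been started, and an event in screening cannot contribute to a Treatment or Allocated Treatment analysis.

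**Working it through.** The plan gives no figure on this point, so there is none to reproduce. The check applies the rule as written and measures how much on-treatment time it exposes.

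**1. The rule applied to single cases.** Take consent on 19 February 2018 and randomisation on 5 March 2018, so that screening runs from 19 February to 4 March.

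| Start date recorded | End date | Phase under SAP 7.2.1 |
|---|---|---|
| March 2018 | 28 March 2018 | Screening |
| 2018 | 20 November 2018 (260 days after randomisation) | Screening |
| Wholly missing | 20 November 2018 | Treatment |

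A patient with consent on 12 February and randomisation on 1 March is not affected by the month rule: screening ends on 28 February, and an event dated March goes to treatment. Likewise, randomisation on 1 January escapes the year rule.

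**2. On-treatment days exposed.** Inputs: 40 weeks of treatment for Regimens B and C (SAP 1.5) plus the 7 days that SAP 5.2 adds to the phase, so 40 × 7 + 7 = 287 days. Assumptions: randomisation dates spread evenly over 2017–2019 (no leap year), consent 7, 14 or 28 days earlier (the Protocol allows up to four weeks), and each event ending 5 days after onset.

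*Day missing.* For randomisation on day k of a month with L days, the on-treatment days in that month number L − k + 1 for k ≥ 2. All of them map to screening; for k = 1 none do. Summing over k gives L(L − 1)/2 for each month:

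- 31-day months: 465 each, seven of them = 3,255
- 30-day months: 435 each, four of them = 1,740
- February: 378
- Mean: (3,255 + 1,740 + 378)/365 = 5,373/365 = 14.7 days, and 14.7/287 = 5.1%
- Range 0 to 30 days; all randomisation dates except the 1st of a month are affected (96.7%)

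*Day and month missing.* For randomisation on day j of the year (j ≥ 2), the exposed days are the smaller of 366 − j and 287:

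- Sum of 1 to 287 = 41,328
- 77 further dates capped at 287 = 22,099
- Mean: (41,328 + 22,099)/365 = 63,427/365 = 173.8 days, and 173.8/287 = 60.5%
- Range 0 to 287 days; all dates except 1 January are affected (99.7%)

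Running the rule over every date gave the same results, and the length of screening made no difference. If instead the default were treatment unless the event ended before randomisation, as in the third rule, none of the 287 days would map to screening.

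These are shares of onset days, and they matter only for events with a partial date. They are not shares of all events.

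**3. Effect on a proportion (illustration).** The documents do not say how many events have partial dates. Assume 200 patients per arm (the Stage 2 target) and a grade 3 or greater proportion of 48.2% (Regimen B in Stage 1, Protocol 2.1.1), so 96.4 patients with an event. If a fraction f of them loses its only qualifying event, 96.4 × f patients are lost and the proportion becomes 48.2% × (1 − f).

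| f | Patients lost | Proportion |
|---|---|---|
| 0.5% | 0.5 | 48.0% |
| 1% | 1.0 | 47.7% |
| 2% | 1.9 | 47.2% |
| 5% | 4.8 | 45.8% |
| 10% | 9.6 | 43.4% |

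Each patient lost lowers the arm's proportion by 1/200 = 0.5 percentage points.

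**The case against.** The mechanism is not in dispute on the text. The case on the other side is about reach and size, and much of it stands.

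- **Reach.** A reader might infer that these events vanish from every safety endpoint. The documents do not support that. Loss is certain only in the Treatment and Allocated Treatment analyses. The whole study period is not defined by phase, and SAP 5.8 defines treatment-emergence by worsening from baseline without expressly excluding screening. The title of SAP 7.2.3 points towards exclusion but does not settle it. All-cause mortality (SAP 7.2.2) does not depend on event placement.
- **Number.** Any grade 3 or greater event is a notable event (Protocol 13.1.3), to be notified within one working day of the site becoming aware (Protocol 13.2.1(d)). Visits are weekly to Week 4 and then 4-weekly to Week 52. Laboratory, ECG and audiometry findings come from dated tests. A year-only onset for a severe event is hard to picture, so the 60.5% figure should not be read as typical.
- **The month rule is not always unreasonable.** With consent on 5 March and randomisation on 19 March, screening covers 14 days of that month and treatment 13, so screening is the likelier phase by days (14/27 = 52%). The year rule has no such defence: with consent on 1 February and randomisation on 1 March, screening is 28 of 334 days (8%), yet every such event goes there.
- **Comparison.** A reader might also infer a biased difference between arms. None is shown, because the same rule applies to both. Regimen B has an injectable in the intensive phase and Regimen C does not, so equal loss cannot be assumed, but that is not evidence of unequal loss.
- **Conservatism.** SAP 5.8 calls its handling of day-1 laboratory events conservative, but that sentence covers only those events and is not a general principle. At the boundary between treatment and follow-up, the earliest-phase rule is itself conservative, because it puts ambiguous events in treatment.

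None of this removes the inconsistency with the third rule or the loss from the two phase-based analyses.

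**Conclusion.** The point holds in limited form. As written, SAP 7.2.1 places an event known only to the month or year of randomisation in screening whenever screening overlaps that month or year, whatever its end date on treatment. It is then lost from the Treatment and Allocated Treatment analyses in SAP 7.2.3 and 9.3.5. Whether it is also lost from the main comparison turns on a term the SAP leaves undefined.

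The direction is to understate on-treatment events in each arm. The size cannot be fixed from the documents: it depends on an unreported number of partial dates, which is probably small for grade 3 or greater events, and a patient leaves a proportion only if no other qualifying event remains. The exposure figures rest on the assumed calendar and planned treatment length, and the proportions in the last table on assumed loss fractions. The primary efficacy outcome is untouched. The rule merits correction because it gives a wrong placement for some events and is easily repaired, not because a distorted treatment comparison has been demonstrated.

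**What to change.** In the first two rules of SAP 7.2.1, place the event in the earliest phase starting on or after randomisation that overlaps the known month or year, and keep the exclusion of phases that start after the event's end date. Use screening only if the known month or year, or the end date, shows that onset was before randomisation. Restricting the choice to phases that overlap the known date matters: a plain default to treatment would put an event dated 2020 into treatment for a patient whose treatment ended in 2018.

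In SAP 7.2.3 and 9.3.5, state that the whole study period for adverse event analyses runs from randomisation.

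The cost is a few lines of SAP text and a small programming change. Where tables have already been produced, rerun them and report the number of reassigned events by arm, which would also show whether the issue mattered. The downside is that a few true screening events will be counted as on-treatment, which is the cautious direction for safety.

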7.2.2 All-cause mortality during treatment or follow-up

All-cause mortality is defined as a patient who has died from any-cause (both TB- or non-TB-related) while in the trial either during treatment or during follow-up.

The number of patients who die during treatment and follow-up will be tabulated by treatment arm. Mortality rates, stratified by randomisation protocol and HIV status, will be calculated for the individual treatment arms and treatment group differences in mortality rates will be calculated together with a 95% confidence interval. For patients that do not die, time will be censored at their final visit.

The difference in proportion of patients dying during treatment and follow-up, between Regimen B and Regimen C, between Regimen B $_{\text{mox}}$ and Regimen C, between Regimen B and Regimen D, and between Regimen B and Regimen A, with corresponding two-sided 95% confidence intervals and p-values will be estimated (see Section 6.1.1). The analysis will be stratified by randomisation protocol (as defined in Section 1.6) and HIV status with three strata: HIV negative, HIV positive with CD4 count less than 350 cells/mm³, and HIV positive with CD4 count more than or equal to 350 cells/mm³.

Survival analysis will be conducted for time to death. A hazard ratio with corresponding two-sided 95% confidence intervals and p-value will be estimated for the comparison of

Regimen B with Regimen C, and Regimen B with Regimen D, using a Cox Proportional Hazards model stratified by randomisation protocol (as defined in Section 1.6) and the randomisation stratification factor HIV status with the three categories of: HIV negative; HIV positive with CD4 count ≥350 cells/mm³; and HIV positive with CD4 count <350 cells/mm³.

The equality of survivor functions for time to death for Regimen B and Regimen C, and Regimen B and Regimen D, will each be tested using a Log rank test, stratified by randomisation protocol (as defined in Section 1.6) and the randomisation stratification factor HIV status with the three categories of: HIV negative; HIV positive with CD4 count ≥350 cells/mm³; and HIV positive with CD4 count <350 cells/mm³.

This analysis will be conducted on the whole study period, and separately for follow-up censored at Week 76. It will also be repeated comparing bedaquiline and non-bedaquiline regimens (Regimens A and B vs C and D) and comparing Regimen B_{mox} and Regimen C, and Regimen B_{lev} and Regimen C. A descriptive analysis will consider deaths by cause, as adjudicated by an independent review committee. In addition to the comparisons detailed above, analyses of the whole study period (up to Week 132) will include comparisons of Regimen C with Regimen D. Comparisons of Regimen C and Regimen D using data up to Week 76 were carried out at the time of the primary analysis but considered exploratory.

7.2.3 Proportion of patients experiencing a grade 3 or greater adverse event, as defined by the DAIDS criteria, during treatment and follow-up

The difference in proportion of patients experiencing a grade 3 or greater adverse event, as defined by the DAIDS criteria¹⁰, during treatment and follow-up, between Regimen B and Regimen C, between Regimen B_{mox} and Regimen C, between Regimen B_{lev} and Regimen C, between Regimen B and Regimen D, and between Regimen B and Regimen A, with corresponding two-sided 95% confidence intervals and p-values will be estimated (see Section 6.1.1). The analysis will be stratified by randomisation protocol (as defined in Section 1.6) and HIV status with three strata: HIV negative, HIV positive with CD4 count less than 350 cells/mm³, and HIV positive with CD4 count more than or equal to 350 cells/mm³.

This analysis will be conducted on the whole study period, the study period censored at Week 76, and separately for each phase (Treatment censored at Week 76, and Allocated treatment).

Comparisons will be repeated in subgroups according to HIV infection status. In addition the proportion of participants with cardiac events, hearing loss and hepatotoxicity by Week 76 and Week 132 in Regimen C and Regimen D will be compared to Regimen B.

In addition to the comparisons detailed above, analyses of the whole study period (up to Week 132) will include comparisons of Regimen C with Regimen D. Comparisons of Regimen C and Regimen D using data up to Week 76 were carried out at the time of the primary analysis but considered exploratory.

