#### 1.1.6 Duration of follow-up

All patients in Stage 1 of the study will be followed up to Week 132. The primary analysis will be based on the data accrued to Week 132.

All patients in Stage 2 of the study will also be followed up to Week 132, 56 weeks beyond the primary analysis point at Week 76. The main purpose of this extended follow-up is to monitor safety outcomes, particularly deaths. Recruitment to Stage 2 was slower than initially expected, as several sites closed to recruitment early due to their NTP adopting a fully oral regimen in line with changing WHO Guidelines. Given the urgent need for evidence to contribute to global guidelines on all-oral treatment regimens, with Version 11 of the protocol the end of follow-up for efficacy has been brought forward, although follow-up for safety is unchanged; follow-up for efficacy will end when the last patient recruited is projected to have reached Week 96. This will allow microbiology results to be

complete by the end of the trial, facilitating rapid analysis and reporting of Stage 2 results. The impact of shortening the follow up period for efficacy is minimal, and outweighed by the benefits of earlier availability of long-term trial results. The majority of patients (approximately 75% on Regimens B and C) will still have efficacy outcomes at Week 132, but for a proportion of patients (those randomised towards the end of the recruitment phase) efficacy follow-up will be censored between 96 and 132 weeks. The reduction in the total person-years of follow-up for the efficacy analysis is small, only 3% in Regimens B & C.

In summary, in Stage 2 the primary analysis will be based on the data accrued to Week 76; the data accrued to the date when the last patient is projected to have reached Week 96 will be used for the secondary long-term efficacy analysis and all data to the end of trial at Week 132 will be used for the long-term safety analyses.

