## 8.5.5 Follow-up of patients discontinued from treatment

Every effort should be made to follow up all patients for the full duration of the study, including those whose treatment is discontinued or whose treatment is changed. A reduced frequency of follow up may be appropriate, and if necessary, should be agreed with the MRC CTU. In this event, a final status form should be completed. For patients who have discontinued follow-up visits, but have not withdrawn consent, the vital status should be obtained at least every six months until Week 132, if necessary by telephone follow up.

If a patient can be contacted and declines further study participation, an investigation into their reasons will be conducted, and the reasons documented. An attempt will be made to have him/her come to the clinic for a final visit, or at least obtain a sputum sample for the assessment of the primary efficacy outcome.

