For the primary analysis of Stage 2, the difference in favourable outcome rate between Regimen B ( $B_{mox}$  and  $B_{lev}$  combined) and Regimen C with corresponding two-sided 95% confidence interval and p-value will be estimated using a stratified analysis of the risk difference from each stratum using Cochran-Mantel-Haenszel weights. For Regimen C, non-inferiority will be shown if the upper bound of the 95% confidence interval of the difference in proportion of favourable outcomes is less than the 10% margin of non-inferiority; this must be shown in both the mITT and PP populations. The analysis will be stratified by HIV status with three strata: HIV negative, HIV positive with CD4 count between 50 cells/mm³ and less than 350 cells/mm³, and HIV positive with CD4 count more than or equal to 350 cells/mm³.

The secondary non-inferiority outcome at Week 132 for Regimen B compared to Regimen C will be analysed using time to unfavourable outcome, thereby using information on all participants. Data from participants whose scheduled last efficacy visit is before Week 132 will be censored at the time of their last visit, unless they have already become unfavourable. Non-inferiority must be shown in both the mITT and the PP populations. A sensitivity analysis will estimate the proportion unfavourable at Week 132 on the subset of participants randomised at least 132 weeks on or before 30 November

2021. For the superiority comparisons e.g. of Regimen C compared to Regimen B, at Week 76 and Week 132 only the mITT analysis will be considered.

Mortality rates will be calculated for the individual treatment arms and treatment group differences in mortality rates will be calculated together with a 95% confidence interval. In addition, the number of deaths, per-patient years of exposure will be calculated by treatment arm.

Differences in proportions with Grade 3 or greater adverse events will be compared and 95% confidence intervals calculated for overall comparisons, and repeated in subgroups according to HIV infection status and drug resistance patterns.

ECG data for safety analyses for Stage 2 will be from the central cardiology reading facility for the study.

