2 SAMPLE SIZE

2.1 Power to demonstrate non-inferiority in the primary efficacy outcome (primary objective relating to Regimens B and C)

Stage 2 aimed to randomise at least 200 patients to each of Regimen B (B_{mox} or B_{lev}) and Regimen C. This revised sample size in protocol version 8.0 was determined based on the assumption that the proportion of patients with a favourable efficacy outcome at Week 76 is 80% for Regimen B (estimated based on preliminary Stage 1 results) and 82% for Regimen C (based on an anticipated minimum benefit in efficacy of using 40 weeks treatment with bedaquiline compared to 16 weeks treatment with kanamycin). Using a non-inferiority margin of 10% and a one-sided significance level of 2.5%, 172 evaluable patients will be required in each of the two regimens to demonstrate non-inferiority of Regimen C to Regimen B with 80% power. To account for 14% of patients excluded from the primary per protocol efficacy analysis population, a total of 400 patients will need to be enrolled across the 2 regimens.

A sample size of 400 patients enrolled to the comparison of Regimens B and C is necessary to rule out an 8% increased mortality in Regimen C compared to the 8% observed on Regimen B in the preliminary analysis of STREAM Stage 1. This will provide 80% power with a one-sided 0.025 type I error.

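### Mortality time at risk depends on outcome: deaths count throughout follow-up, but survivors are censored at their final visit

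*SAP*

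**What the plan says.** SAP 7.2.2 defines all-cause mortality as death from any cause "while in the trial either during treatment or during follow-up". It then gives one censoring rule: "For patients that do not die, time will be censored at their final visit". The section specifies mortality rates and their differences, a stratified difference in the proportion dying, a Cox hazard ratio and a stratified log-rank test. On the period covered it says "This analysis will be conducted on the whole study period, and separately for follow-up censored at Week 76". Protocol 11.6 adds that "the number of deaths, per-patient years of exposure will be calculated by treatment arm".

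Two other passages govern how long a patient is observed for death:

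- SAP 5.2 ends the follow-up phase at the "date of the last patient contact (scheduled or unscheduled visit, or other contact e.g. phone call").
- Protocol 8.5.5, for patients who no longer attend but have not withdrawn consent, says "the vital status should be obtained at least every six months until Week 132, if necessary by telephone follow up".

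Final visit is not defined in SAP 7.2.2, and SAP 5.2 lists visits and phone calls as different kinds of contact.

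**The concern.** Read together, these passages give deaths and survivors different ends of follow-up. Suppose two patients stop attending at Week 40 and both are traced by phone. One dies at Week 100 and enters as an event at Week 100 with 100 weeks of time at risk. The other is confirmed alive at Week 132 and is censored at Week 40. The same kind of contact adds time at risk only when its answer is that the patient has died. This is not ordinary non-informative censoring, because the censoring time depends on the outcome.

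The affected measures are those that use time: the person-time rates, their differences, the Cox hazard ratio and the log-rank test. Protocol 1.1.6 says of follow-up beyond Week 76: "The main purpose of this extended follow-up is to monitor safety outcomes, particularly deaths". The rule discards survivor time collected for that purpose. It could also make the rates and the hazard ratio disagree with the difference in proportions for no reason other than the censoring rule.

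**Working it through.** **The plan's own mortality figure.** SAP section 2 says 400 patients are needed to "rule out an 8% increased mortality in Regimen C compared to the 8% observed on Regimen B", with 80% power at one-sided 0.025. As non-inferiority on a difference in proportions:

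n per arm = (1.960 + 0.842)² × 2 × 0.08 × 0.92 / 0.08² = 180.5, so 181 per arm.

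Dividing by 0.90 gives 202 per arm, 404 in total. The 400 therefore reproduces closely with an allowance of about 10%, which the mortality sentence does not state. It rests on proportions, uses no follow-up time and is not affected by the censoring rule.

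**Inputs for the effect of the rule**

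- From the SAP: 8% mortality on Regimen B. That it applies by Week 132 is an assumption.
- Assumed, because the documents give no figure: 5–30% of patients stop visits, all at Week 40 or all at Week 76; stoppers and attenders have the same death hazard; vital status is complete (upper bound) or known for half of stoppers.

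**Rate per arm.** With exponential deaths, λ = −ln(0.92)/132 = 0.000632 per week. Mean time to death or Week 132 is 0.08/λ = 126.65 weeks. With 52.18 weeks per year, the true rate is 0.08/126.65 × 5218 = 3.30 per 100 person-years.

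Under the final-visit rule, a traced survivor who stopped at week w loses 132 − w weeks. If a share s stops:

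rate = 0.08 / [126.65 − s × 0.92 × (132 − w)] × 5218

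For s = 30% and w = 40: 0.08 / (126.65 − 25.39) × 5218 = 4.12.

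| Share stopping | Week 40, all traced | Week 76, all traced | Week 40, half traced | Week 76, half traced |
|---|---|---|---|---|
| 5% | 3.41 | 3.36 | 3.35 | 3.33 |
| 10% | 3.53 | 3.44 | 3.41 | 3.37 |
| 20% | 3.80 | 3.59 | 3.55 | 3.44 |
| 30% | 4.12 | 3.75 | 3.71 | 3.53 |

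Against 3.30, this is +2% to +25% with complete tracing and +1% to +13% with half traced. A separate simulation with complete tracing spread the stopping times. For 5–30% stopping it gave +2.4% to +16.2% over Weeks 4–132 and +4.1% to +31.5% over Weeks 4–40.

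**Hazard ratio when true mortality is equal.** After week w, the share of an arm still at risk is S(t) − 0.92s, while deaths continue at λS(t). The apparent hazard ratio (C v B) after week w is therefore (S − 0.92 s_B)/(S − 0.92 s_C); before week w it is 1.

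Hand check for 20% in B and 10% in C, stopping at Week 40:

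- S falls from 0.975 to 0.92; take 0.9475 as the midpoint.
- The later ratio is (0.9475 − 0.184)/(0.9475 − 0.092) = 0.892.
- About 69% of deaths fall after Week 40, since (0.975 − 0.92)/0.08 = 0.69.
- The overall hazard ratio is about exp(0.69 × ln 0.892) = 0.92.

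Cox results on 1.5 million simulated patients per arm, all traced:

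| Stopping, B v C | Week 40 | Week 76 |
|---|---|---|
| 10% v 10% | 1.00 | 1.00 |
| 15% v 5% | 0.93 | 0.96 |
| 20% v 10% | 0.92 | 0.96 |
| 30% v 20% | 0.92 | 0.95 |
| 10% v 20% | 1.08 | 1.05 |
| 30% v 10% | 0.85 | 0.91 |

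Solving the expression above numerically agrees with these to within 0.01. With half traced, a 10-point excess in B gives 0.95–0.98.

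**Log-rank test.** Unstratified, 20,000 simulated trials of 200 per arm, nominal 5%. Under the final-visit rule, type I error is 5.3–5.7% for a 10-point imbalance; for 30% v 10% it is 8.2% (Week 40) or 6.3% (Week 76). Censoring at the date last known alive gives 4.7–5.3% in every scenario. The mean difference in proportions is 0.0 points throughout.

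**The case against.** The strongest reply is that the SAP never says in one sentence that deaths learned of after visits stop are counted. If final visit is read as last contact, the problem disappears. That reading is possible, but SAP 5.2 separates visits from phone calls, and no passage excludes later deaths from an analysis that runs over the whole study period. If last contact is what is meant, the proposed sentence simply records it.

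The censoring sentence also sits in the paragraph on rates, and the Cox and log-rank paragraphs state no rule of their own. Applying it to them is an inference, but it is the only censoring rule given for survivors.

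On size, the reply has weight. With 8% mortality in 400 patients there are about 32 deaths, so the standard error of the log hazard ratio is about √(4/32) = 0.35. A hazard ratio of 0.92–0.96 is then a shift of only 0.12–0.24 standard errors. The larger distortions need 30% v 10% stopping, and nothing in the documents suggests a difference by arm. Mortality is a secondary outcome, and SAP 7.2.2 attaches no decision rule to the hazard ratio.

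The proposed rule is not perfect either. Contacts may be six months apart, and a death may be reported for someone otherwise untraced, so some asymmetry would remain. Finally, the SAP's revision history moves further mortality sensitivity analyses to the Extensive SAP, which was not available here. A sensitivity analysis there would not correct the rule in this SAP.

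**Conclusion.** The concern holds. Followed as written, SAP 7.2.2 makes time at risk depend on outcome for patients who stop visits but remain under vital-status follow-up. Arm-specific mortality rates are overstated whenever such patients are traced: by 1% to 25% over the assumed range of 5–30% stopping at Week 40 or 76, and by more if stopping is earlier. The hazard ratio and log-rank test are biased only if stopping differs by arm, which an open-label design permits but the documents neither show nor exclude. A 10-point imbalance moves a true hazard ratio of 1.00 by roughly 0.04 to 0.08 with complete tracing and by about half that with half traced.

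Death counts, the stratified difference in proportions and the mortality sample-size statement are unaffected. This should be corrected, but it does not threaten the trial's primary conclusion. Confidence in the size is moderate, because the share stopping visits is assumed.

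**What to change.** Replace the censoring sentence in SAP 7.2.2 with wording such as: *Patients not known to have died will be censored at the date last known alive, whether established at a visit, by telephone or by other vital-status contact, and no later than Week 132 (Week 76 for the Week 76 analysis). Deaths after the same cut-off will not be counted as events in that analysis.* State that this applies to the person-year rates, the Cox models and the log-rank tests.

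Because tracing may be incomplete, a useful optional addition is a sensitivity analysis that ends follow-up at the final visit for deaths and survivors alike.

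The main change costs one sentence in the SAP. Protocol 8.5.5 already calls for the vital-status contacts, so no new data collection is needed.
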